The survey takes 10-15 minutes to complete and includes 42 items used to derive 12 composite measures (**Table 8**), 2 single-item measures, and respondents' backgrounds (unit, staff position, interaction with patients, years of experience in current profession, hospital, and current nursing unit). Most items are scored on a scale from 1 (strongly agree) to 5 (strongly disagree). Creating composite scores involves: (1) inverting the scales of any negatively worded items, (2) identifying positive responses (1 or 2); (3) calculating the percent of responses that were positive for each item (excluding missing values), and (4) averaging the percent positive across all items within a composite measure.

The two composite measures we plan to use are directly relevant to incident reporting and likely to be responsive to system-level changes. *Feedback and Communication About Error* includes three items: staff are informed about errors, discuss ways to prevent errors, and are given feedback about changes implemented. The *Frequency of Events Reported* also includes three items: staff report mistakes that are caught before affecting the patient, with no potential to harm, and that could harm but did not. In a prior analysis from three nursing units at three different hospitals, scores on these two composite measures were correlated ($\rho=0.56$) but factor analyses indicated that they captured distinct concepts (loaded separately). Respectively, Cronbach α values for these measures were 0.77 and 0.78 among nurses, demonstrating good internal consistency.⁵⁵

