B. Data Collection: Cedars-Sinai routinely surveys staff every two years using the Hospital SOPS. For the study, we will survey ~1980 eligible nurses on study nursing units twice via 4 total deployments of the full Hospital SOPS during two-week intermissions between study periods (Section 3A). To identify eligible nurses, we will obtain staffing databases including names, email addresses, title/position, percent effort, dates of work on the unit, and work schedule. At least 85% of nurses on study units will be eligible. Two weeks before deployment, we will send email notices to expect the survey and a researcher will visit nursing units to reinforce survey completion. The survey will be delivered via REDCap using a weblink embedded in an email. During each deployment, we will deliver the survey three times. We will incentivize completion at the individual (lotteries for iPads) and unit levels (gift baskets of snacks for response rates >65%). To minimize detection bias, the survey will not refer to the SAFE Loop intervention. To avoid having incomplete outcome data, we will monitor survey response rates and make adjustments to procedures as needed.

Methods for Aim 3: Rates of Target Medication Events

A. Measures: The primary outcome will be the *rate per 1,000 patient-days of Target Medication Events (preventable plus potential adverse drug events)* selected by the 10 nursing units in Groups 1 and 3. We will also examine the rate of events involving harm. We will define events as in prior research (**Table 10**).^{38,61,62}

Table 10: Medication Event Definitions		Examples
ADE (NCC MERP severity E-I)	A patient injury* resulting from a medical intervention related to drug(s).	A rash due to an antibiotic.
Preventable	An adverse drug event due to a medication error. †	A rash due to an antibiotic given despite known allergy.
Non-preventable	An adverse drug event not due to an error.	A rash occurring after first exposure to an antibiotic.
Potential ADE	A medication error that had the potential to cause injury but did not.	
Intercepted (NCC MERP B)	A medication error that was detected and stopped before the patient received the medication.	A pharmacist filling orders discovers a known allergy and prompts the prescriber to switch antibiotics.

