Power calculations are the same for both composite outcome measures. The baseline percentages of positive responses are 75% (H2.1) and 72% (H2.2). We assume 85% of 1980 nurses will be eligible and a 60% response rate (50.5 responses per nursing unit per deployment). We also assume a discrete uniform distribution for each composite measure with only four possible values (0%, 33%, 66%, 100%) per nurse because each measure contains 3 items. Therefore, we assume standard deviation (SD) equal to 37%, and a between-cluster coefficient of variation of 0.65 as recommended by Campbell and Walters.² The **Table** presents the minimum detectable difference in the percentage of positive responses as a function of the intra-cluster correlation (ICC) and presence of implementation trend, using a two-sided t-test for Normal means with 80% power at 5% significance level. Based on prior studies, a meaningful difference in the percentage of positive responses is 8.6 percentage points (pp).³ Missing data patterns will be examined using the method proposed by Little⁴ if the data is found to be not missing at completely random, missing values will be imputed with values drawn from fully conditional specifications using the multivariate imputation by chained equations (MICE) algorithm,^{5,6} with the number of imputed datasets chosen such that the maximum loss of efficiency of 5%.⁷ The plausibility of imputed values will be checked by corresponding diagnostics. The outlined statistical analysis will be performed for each imputed dataset and results will be pooled. All hypotheses will be two-sided at 5% significance level. Calculations will be performed using R-package, version 3.5.3.

Implementation trend	Intra-cluster Correlation			
	0.01	0.05	0.10	0.20
Yes	10pp*	11pp	12pp	13pp
No	7pp	8pp	10pp	11pp

¹ [name] TK, Bell DS, Paddock SM, Hilborne LH. Contributing factors identified by hospital incident report narratives. Qual Saf Health Care. Oct 2008;17(5):368-372.

² Campbell MJ, Walters SJ. How to design, analyse and report cluster randomised trials in medicine and health related research. John Wiley & Sons; 2014.

³ Campione J, Famolaro T. Promising Practices for Improving Hospital Patient Safety Culture. Jt Comm J Qual Patient Saf. Jan 2018;44(1):23-32.

⁴ Little RJ. A test of missing completely at random for multivariate data with missing values. Journal of the American Statistical Association. 1988;83(404):1198-1202.

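### If Aim 2 imputation is run, the 5% efficiency-loss rule permits so few imputed data sets that a borderline H2.1 result could change significance with the random seed

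*Combined protocol and SAP*

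**What the plan says.** The missing-data method for Aim 2 stands in Section 9.2, within the sample-size text. The missing-data pattern is tested first, and "if the data is found to be not missing at completely random, missing values will be imputed" by chained equations, "with the number of imputed datasets chosen such that the maximum loss of efficiency of 5" percent. The analysis is then run on each imputed data set and the results are pooled. Tests are two-sided at 5%.

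No minimum m, random seed, Monte Carlo error criterion or expected FMI is given. The Aim 2 part of Section 9.4.2 adds nothing on imputation. H2.1, the Feedback and Communication About Error composite, is the primary outcome for Aim 2 (Sections 3 and 9.1).

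On the amount of missing data, Section 9.2 states: "We assume 85% of 1980 nurses will be eligible and a 60% response rate (50.5 responses per nursing unit per deployment"). Section 8.1 scores the composites by "calculating the percent of responses that were positive for each item (excluding missing values").

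**The concern.** A cap on efficiency loss controls average precision: 5% more variance costs little power. It does not control whether one reported p-value would recur under another seed. At the smallest m that the rule allows, a few percent of the total variance of the pooled estimate is simulation noise. Two analysts who both follow the plan, with different seeds, would report somewhat different estimates, intervals and p-values for the Aim 2 primary outcome. With no seed stated in advance and m open above the minimum, either could also be chosen after results are seen, a freedom that is easy to remove.

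**Working it through.** **Inputs.** From Section 9.2: 1,980 nurses, 85% eligible, 60% response, 20 units, efficiency loss of at most 5%, two-sided 5% tests. Assumed, because the documents do not give it: FMI of 0.2 to 0.5 if the 40% non-response is imputed, and 0.02 to 0.10 if only item gaps are.

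**The plan's own figure.** 1,980 × 0.85 × 0.60 / 20 = 50.49, which reproduces the stated 50.5 responses per unit per deployment.

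**Number of imputations.** Relative efficiency is 1/(1 + FMI/m). Requiring at least 0.95 gives m ≥ 19 × FMI. The simpler form, FMI/m ≤ 0.05, gives m ≥ 20 × FMI. Rounded up, both give the same integers, with a minimum of 2 because pooling needs two data sets.

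**Seed noise.** Write B for the between-imputation variance and T for the total variance. Then B/T = FMI/(1 + 1/m), and the Monte Carlo variance of the pooled estimate is B/m. In standard-error (SE) units the seed SD is therefore √[FMI/(m + 1)].

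| Assumed FMI | Smallest m allowed | Seed SD (SE units) | Seed SD at m = 50 |
|---|---|---|---|
| 0.02 | 2 | √(0.02/3) = 0.08 | 0.02 |
| 0.05 | 2 | √(0.05/3) = 0.13 | 0.03 |
| 0.10 | 2 | √(0.10/3) = 0.18 | 0.04 |
| 0.2 | 4 | √(0.2/5) = 0.20 | 0.06 |
| 0.3 | 6 | √(0.3/7) = 0.21 | 0.08 |
| 0.4 | 8 | √(0.4/9) = 0.21 | 0.09 |
| 0.5 | 10 | √(0.5/11) = 0.21 | 0.10 |

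These figures cover the estimate only. A simulation of Rubin's rules (400,000 draws) that also let the between-imputation variance vary gave a seed SD for the test statistic near 1.96 of 0.27 to 0.32 at FMI 0.2 to 0.5 with the smallest m, so the table is on the low side for the p-value.

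**Effect on a borderline p-value.** Take a statistic of 2.0 and a seed SD of 0.21. The 95% seed range is 2.0 ± 1.96 × 0.21, that is 1.588 to 2.412.

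- Normal reference: p = 0.046 at 2.0, with a range of 0.016 to 0.11.
- t with an assumed 18 df (20 randomised units less 2): p = 0.061 at 2.0, with a range of 0.027 to 0.13.

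The plan does not state the analysis degrees of freedom. Both ranges include 0.05.

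**How far from the threshold this reaches (normal reference, SD 0.21).** At 1.76 or 2.16 the chance that a seed crosses 1.96 is P(Z > 0.20/0.21) = 17%. At 1.6 it is about 4% and at 2.4 about 2%. At 2.8 it is close to nil, and about 3% in the fuller simulation.

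**Whether a borderline result is likely.** Section 9.2 calls 8.6 percentage points meaningful, while six of the eight minimum detectable differences in its Aim 2 table are 10 to 13 points. Taken at face value (the table could not be reproduced with the standard formulas tried), a true 8.6-point effect has an expected statistic of 2.80 × 8.6/13 = 1.85 to 2.80 × 8.6/10 = 2.41 in those six. Two seeds would then disagree on significance in about 8% to 9% of trials at a seed SD of 0.21, against about 3% to 4% at m = 50.

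**The case against.** The strongest reply is that the plan already pre-specifies a quantitative rule with a citation, and that pooling by Rubin's rules adds B/m to the variance. Intervals widen to reflect a finite m, so there is no bias and no shown inflation of type I error. This stands. A reader might infer that the H2.1 inference is invalid or cannot be reproduced. The documents do not support that: the inference stays valid, and any recorded seed reproduces its own result.

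Four further limits stand.

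- Imputation is conditional on the test for missing completely at random. Seed noise is therefore not a feature of the H2.1 test in every case.
- The rule is a ceiling on the loss, so any larger m complies. The plan simply does not commit to one.
- The 4 to 10 range depends on an FMI that the documents do not give. It fits imputing non-respondents, but the planned sample size counts respondents only, Section 7.3 says that not completing the survey is not loss to follow-up, and composites are scored without missing items. If only item gaps are imputed, the range does not apply.
- A reader might take the noise to be about 0.2 SE whatever the FMI. At m = 2 it falls to 0.08 SE at an FMI of 0.02.

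What does not stand is that a conditional analysis can be left loosely specified. Once triggered, it produces the Aim 2 primary result.

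**Conclusion.** The point holds as an inexpensive improvement, not as a flaw in validity. If imputation is triggered, the 5% rule allows as few as 4 to 10 data sets at an assumed FMI of 0.2 to 0.5, with a seed SD of about 0.20 to 0.21 SE in the H2.1 estimate. At an assumed FMI of 0.02 to 0.10 it allows 2, with about 0.08 to 0.18 SE. Only a result near the threshold is exposed. It is tempting to conclude that the seed decides significance in general, but clear results would rarely change. Severity is minor (nice to have). Confidence is medium, because the FMI, the scope of the imputation and the reference degrees of freedom are all assumed.

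**What to change.** In the Aim 2 missing-data text of Section 9.2, or better in Section 9.4.2, replace the 5% efficiency rule with three statements:

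1. a fixed m, for example 50;
2. the random seed, stated before the data are analysed;
3. a commitment to raise m if needed until the Monte Carlo error of the H2.1 estimate is below 10% of its standard error.

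The third needs about m = 100 × FMI, that is 20 to 50 data sets for an FMI of 0.2 to 0.5, so 50 covers that range with little to spare. The cost is SAP wording and longer computing time, which may be noticeable for multilevel imputation. Design, sample size and participants are unaffected.

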9.3 POPULATIONS FOR ANALYSES

The trial will randomize 20 nursing units to two arms: (1) the SAFE Loop, and (2) the existing reporting system (control). All analyses will compare data between these two arms.

9.4 STATISTICAL ANALYSES

9.4.1 GENERAL APPROACH

We will employ a cluster RCT to compare nursing units that implement the SAFE Loop, a system-level change in incident reporting, with nursing units that continue to use the existing reporting system. Outcomes will include changes in incident reporting practices, nurses’ attitudes toward reporting, and rates of high-priority medication events. Qualitative interviews with nurses will provide insight into implementation. See Section 9.4.2 for detailed information describing the analytic plan.

9.4.2 ANALYSIS OF THE PRIMARY EFFICACY ENDPOINT(S)

Aim 1 Analyses:

Descriptive Analysis: We will perform descriptive analyses of reporting practices during the baseline periods and intervention periods, stratified by study arm. We will calculate rates of reported Target Medication Events and total reported medication events per 1000 patient-days (# of reports*1000/# of patient-days). Next, we will calculate the percentages of reported incidents in each NCC MERP category and the percentages of reports for which preventability could be determined. Finally, we will calculate

the number of contributing system, human, and patient factors per report and describe the types of factors reported.

Statistical Analyses: We will compare changes over time between study arms for: (a) rate of incident reports per 1000 patient-days, and (b) number of system plus human factors per report. Multivariable Poisson regression models will be fitted with response variables as (a) number of reports per patient, with offset given by the length of stay divided by 1000; and (b) number of system plus human factors per report. For both models, the main hypothesis is whether there is an interaction between study arm and time period (baseline, post-intervention). Nursing units will be divided between two implementation steps, creating the possibility of an implementation trend. Therefore, a three-way interaction among study arm, time period, and implementation step (Step 1: Group 1 and 2, Step 2: Group 3 and 4) will be tested. If this is statistically significant, results will be presented separately for each implementation step. Otherwise, implementation step will be an additive effect. Random effects will describe nursing units and models will adjust for demographics, Elixhauser comorbidity index, and primary payer (collected under Aim 3). All hypotheses will be two-sided at 5% significance level. Calculations will be performed in R-package, version 3.5.3.

Aim 2 Analyses:

Descriptive Analysis: We will calculate survey response rates, examine respondent characteristics (years worked in current profession, hospital, and current nursing unit and hours worked per week), and describe outcome measures (overall scores and composite measures) during each study period, stratified by study arm.

Assessment of Survey Measurement Properties: To evaluate the two selected composite measures' internal consistency, we will calculate Cronbach's α using data from baseline survey. To assess construct validity and convergent validity, respectively, we will evaluate associations (Pearson correlation coefficients) between scores on the composite measures and: (1) the full Hospital SOPS, and (2) incident reporting rates at the nursing unit level. To assess responsiveness, we will compare scores from baseline and follow-up surveys among nurses in the SAFE Loop arm (paired t-tests). If the composite measures do not demonstrate good internal consistency, construct, and convergent validity, we will use the full Hospital SOPS.

Statistical Analyses: We will compare changes over time between study arms for Feedback and Communication About Error and Frequency of Events Reported. Multivariable Normal regression models will be fitted for both endpoints and we will test hypotheses similarly to Aim 1. We will adjust for nurse characteristics from the AHRQ survey: years working in this hospital, years worked in current nursing unit, and hours worked per week. We will perform subgroup analyses by years of experience in current profession, because experience has been associated with medication error rates.⁵⁹

Aim 3 Analyses:

Descriptive Analysis: We will calculate rates of preventable ADEs and potential ADEs per 1,000 patient-days, both overall and for the Target Medication Events for the Group 1 and 3 nursing units. We will describe the severity of the events, medication classes, errors, clinicians involved, and stages in drug therapy.

Statistical Analysis: We will compare changes over time between study arms for rates of (a) Target Medication Events per 1000 patient-days and (b) harmful Target Medication Events per 1000 patient-days. Multivariable Poisson models will be fitted with response variable as the number of (a) target medication events and (b) harmful medication events, with offset the length of stay divided by 1000

days. We will test hypotheses similarly to under Aim 1. Model covariates will include patient demographics, biological sex, Elixhauser comorbidity index, and insurance payer.

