2.3 RISK/BENEFIT ASSESSMENT

2.3.1 KNOWN POTENTIAL RISKS

There are two categories of study subjects who will be affected by SAFE Loop:

1. **Nurses** and nursing unit managers who work in the nursing units, and
2. **Patients** who receive care there.

Table of Study Procedures and Associated Risks for Each Group.

Study Procedure	Risks for Nurses	Risks for Patients
1. Organizational Quality Improvement Intervention: Implementation of SAFE Loop in nursing units	Psychological distress or loss of professional reputation may occur if a nurse is blamed for a medication error after an incident report is submitted. Risks are similar to those in usual nursing practice because nurses already submit incident reports.	Medication error. Risks are unlikely but may occur if the nursing units inadvertently implement changes that worsen rather than improve medication safety, as intended.

	To further mitigate the risks, we will train nurses to emphasize reporting of near misses and no-harm events (which are less likely to result in punitive responses by unit managers) and train unit managers in the “just culture” approach, which emphasizes changing systems of care rather than blaming individual nurses when medication errors occur.	
2a. Research data collection: nursing work schedules, to assess nurse eligibility for survey	Inadvertent disclosure of individually identifiable information on nursing work schedules. This data source does not include sensitive information.	Not applicable.
2b. Research data collection: surveys of nurses on attitudes toward reporting and patient safety culture	Inadvertent disclosure of individually identifiable information on nursing survey. Survey does not involve sensitive information and it is already routinely deployed in this hospital.	Not applicable.
3. Research data collection: analysis of incident reports to assess rate and quality of reports	Inadvertent disclosure of individually identifiable information. This data source includes sensitive information such as errors that nurses may have committed. Data to be extracted will not include individually identifiable information about nurses.	Inadvertent disclosure of protected health information (PHI). Incident reports contain patient identifiers and PHI. Data to be extracted will not contain patient identifiers aside from randomly assigned study identification numbers to facilitate linkage to other datasets.

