6 STUDY INTERVENTION

6.1 STUDY INTERVENTION(S) ADMINISTRATION

6.1.1 STUDY INTERVENTION DESCRIPTION

The SAFE Loop has **three phases: Engagement, Fact-finding, and Action & Feedback**. Across the three phases, the SAFE Loop has **five Key Attributes**. During all phases, the SAFE Loop Team collaborates with frontline nurses and Unit Managers. During the Fact-finding Phase, the team obtains and integrates information from an AHRQ Patient Safety Organization.

Although the SAFE Loop could apply to any problem, we will focus on medication errors because they are common,³⁴⁻³⁷ occur on diverse nursing units, and can be evaluated using well-established methods. Also, nurses file most incident reports and are uniquely able to detect problems not only during drug administration but also during the ordering, dispensing, and monitoring stages in drug therapy.³⁸

Five Key Attributes Designed to Maximize the Effectiveness of Reporting:

(1) Input from Nurses

(Engagement Phase): Nurses are more likely to report events and adopt innovations addressing safety problems that they find to be particularly common, severe, or preventable.³⁹⁻⁴¹ The SAFE Loop Team, therefore, solicits input from nurses and Unit Managers on which problems to select and solve.

(2) Focus on Selected Target Event (Engagement Phase): To make the best use of investigative resources and obtain enough reports to understand each safety problem, the SAFE Loop focuses on Target Medication Events (errors and adverse events related to a selected, defined problem). These events will involve a particular clinical situation, drug class (e.g., opioids), population (e.g., kidney disease), type of error (e.g., duplicate therapy), and/or system factor (e.g., different protocols in ICU and floor units). Examples include: (1) nurses having challenges reconciling medications after patients go to the operating room, (2) pharmacists dispensing mislabeled medication, and (3) physicians ordering multiple sedating medications concurrently.

(3) Stimulated Time-limited Reporting (Fact-finding Phase): Lack of guidance about what and how to report deters reporting and limits reports' usefulness. The SAFE Loop Team prompts nurses to report many Target Medication Events during a certain period and teaches nurses to write more informative reports.

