(4) Integration of Information (Fact-finding Phase): Because most safety problems are not unique to a particular nursing unit or hospital, the SAFE Loop Team integrates information from incident reports, follow-up investigations, and internal and external sources, including an AHRQ PSO.

(5) Feedback to Nurses (Mitigation Phase): To demonstrate that reports are used and can drive system changes, the SAFE Loop Team provides feedback about medication safety problems and mitigation plans.

[figure not shown]
Implementation of Intervention on an Individual Nursing Unit:

Engagement Phase (4 weeks):

Obtain Input: Nursing units convene daily huddles with their staff to discuss various issues. For three weeks, the SAFE Loop Team will attend one huddle per week to provide information on local safety events and obtain input on problems that frontline nurses believe to be common, severe, and preventable.

To include nurses who work at night and on weekends, the intervention will be disseminated through nursing huddles, which occur at shift change. We will also place fliers approved by the Marketing Dept on tack boards in common areas like break rooms and conference rooms away from public areas.

Select Target Medication Events: Each study nursing unit will select its own unique event. Through discussions with nurses and the SAFE Loop Team, the Unit Manager will choose a medication safety problem with a narrow enough scope to facilitate mitigation through targeted actions (e.g., problems

with opioids). The SAFE Loop Team will define inclusion/exclusion criteria for the unit's Target Medication Event.

Fact-Finding Phase (12 weeks):

Train Nurses: The SAFE Loop Team will train nurses to: (1) submit reports on Target Medication Events (in addition to usual reports); (2) focus on unsafe conditions and near misses, and (3) write detailed narrative descriptions of circumstances they observed leading up to each event. The SAFE Loop Team will train Nursing Unit Managers in a just-culture approach (i.e., addressing system issues rather than blaming individuals).

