8 STUDY ASSESSMENTS AND PROCEDURES

8.1 EFFICACY ASSESSMENTS

Methods for Aim 1: Incident Reporting Practices

A. Measures: There are two key outcome measures and several descriptive measures. One key outcome measure is the *rate per 1000 patient-days of incident reports addressing one of the Target Medication Events*. Ten nursing units will implement the SAFE Loop, leading to 10 Target Medication Events total.

The primary outcome measure will be *the number of system plus human factors per incident report*. In industries where incident reporting has been effective, obtaining insights into contributing system and human factors has been the purpose of reporting. To *characterize system and human factors*, we will use the Human Factors Analysis and Classification System for Healthcare (HFACS-Healthcare).⁴⁴ Introduced in 2001, the HFACS has widely been used to analyze incidents in diverse industries internationally.⁴⁴⁻⁴⁷ More recently, HFACS developers adapted it for use in healthcare settings.⁴⁸ HFACS-Healthcare lists 21 categories of contributing factors within 4 tiers (**Table 6**).⁹ We will also examine the number and diversity of factors reported.

Table 6: Incident Report Characteristics		
Contributing Factors (HFACS, 4 tiers)		
Organizational influences (system factors)		
	Unsafe supervision (system factors)	
	Preconditions for unsafe acts (system)	
		Unsafe acts (human factors)
Severity (NCC MERP, 9 Categories)		
A: Safety hazard (did not involve patient)		
B: Event did not reach patient		
C: Event reached patient, no harm		
D: Monitoring/intervention to prevent harm		
E: Temporary harm requiring intervention		
F: Temporary harm, prolonged hospitalization		
G: Permanent harm		
H: Intervention to sustain life		
I: Death		
Preventability (Brook et al.)		
Definitely or probably preventable		
Definitely or probably not preventable		
Uncertain/unable to determine (added)		

Descriptive Measures: Patient factors also represent opportunities to improve care. To classify *patient factors*, we will use categories from prior work.⁴ Experts consider severity and preventability when prioritizing incidents for follow-up and action.⁴⁹ To classify *severity*, we will use the NCC MERP Medication Error Index.⁵⁰⁻⁵² To classify *preventability*, we will adapt an existing scale.⁵³

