Data Collection: Analysts with clinical experience (e.g., nursing, pharmacy) and training in HFACS-Healthcare will manually review incident reports related to medication issues. Pairs of analysts will independently judge whether each incident matches one of the definitions of Target Medication Events, extract information related to the measures above, and then meet to discuss and reach consensus. A human factors expert ([name]) will adjudicate any ties. Analysts will be blinded to nursing unit, time period, and study arm. Data collection instruments will be adapted from our prior work.^{4,9,54} As part of training, analysts will practice on at least 30 sample reports, consulting with each other and the human factors expert until scores are consistent. To evaluate reliability, we will calculate Cohen’s Kappa for 10% of records.

Methods for Aim 2: Nurses’ Attitudes toward Incident Reporting

Measures: The planned outcome measures include two composite measures from the AHRQ Hospital Survey on Patient Safety (SOPS) Culture™, Version 1.0 (English). AHRQ developed the survey in 2004 to assess the perspectives of frontline providers and staff on patient safety, error, and event reporting. Since then, hundreds of hospitals across the U.S. and internationally have used it. The survey has moderate-to-strong validity and reliability,⁵⁵ and the items and dimensions are psychometrically sound at the individual, unit, and hospital levels.⁵⁶ A 2015 systematic review found associations between Hospital SOPS scores and patient outcomes at hospital and nursing-unit levels of analysis.⁵⁷ Scores represent percentages (range 0-100%, higher is better). Changes in overall Hospital SOPS scores of 8.6 percentage points (range, 6.5-10.6) have been associated with changes in practices by hospital leaders.⁵⁸

Table 8: Hospital Survey on Patient Safety (SOPS) Culture, Including Data from Study Site (CSMC) and Nationally		
12 Composite Measures	CSMC	National
Feedback & Communication About Error	75%	68%
Frequency of Events Reported	72%	67%
Communication Openness	63%	64%
Handoffs & Transitions	52%	46%
Management Support for Patient Safety	72%	73%
Nonpunitive Response to Error	35%	44%
Organizational Learning	83%	73%
Overall Perceptions of Patient Safety	70%	66%
Staffing	49%	53%
Supervisor Expectations & Actions	74%	79%
Teamwork Across Units	66%	61%
Teamwork Within Units	84%	82%

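### The Aim 1 models have no place for reports that involve no patient, although such reports are graded in Aim 1 and SAFE Loop training solicits unsafe-condition reports

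*Combined protocol and SAP*

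**What the plan says.** - **Report set.** In section 8.1, analysts "manually review incident reports related to medication issues" and grade severity in nine categories. The first in Table 6 is "A: Safety hazard (did not involve patient"). No text excludes it from Aim 1.
- **Training.** Section 6.1.1 (Train Nurses) tells SAFE Loop nurses to "focus on unsafe conditions and near misses". Section 2.3.1 describes the emphasis differently: "train nurses to emphasize reporting of near misses and no-harm events".
- **H1.1 numerator.** The endpoint is limited to reports on a Target Medication Event, and section 6.1.1 defines these as "Target Medication Events (errors and adverse events related to a selected, defined problem").
- **Models (section 9.4.2, Aim 1).** The H1.1 response is "number of reports per patient, with offset given by the length of stay divided by 1000". The H1.2 response is the count of system plus human factors in each report. For both, "models will adjust for demographics, Elixhauser comorbidity index, and primary payer".
- **Descriptive rate (same section).** Reports are divided by patient-days, with no link to individual patients.
- **Missing data.** The only rule stands in the Aim 2 part of section 9.2. Aim 1 has none.

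**The concern.** The H1.1 model needs a patient to supply each row and a length of stay to supply the exposure. A category A report has neither. The H1.2 model gives every report a row, but age, comorbidity and payer do not exist for a report without a patient. They are undefined rather than unrecorded, so imputation has no meaning, and a complete-case fit would delete the report.

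This matters because the intervention acts on the type of report filed. If nurses on SAFE Loop units respond to the training with more unsafe-condition reports, the reports lost are partly a product of treatment. H1.1 would then miss part of the increase it is meant to detect. H1.2, the Aim 1 primary outcome, would compare arms on a subset of reports selected after randomisation.

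**Working it through.** **1. Reproduce Table 1.** Inputs from section 9.2: baseline 2.26 reports per 1,000 patient-days; 7,362 patient-days per unit per six months, so y = 7.362 thousand; two-sided 5% level; 80% power. There are 10 units per arm, or 5 per arm per step where a trend is allowed. Solve for d = λ1 − λ0 in

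(c − 1)·d² = (1.960 + 0.842)² × [(λ0 + λ1)/y + CV²(λ0² + λ1²)].

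With c = 10 and CV 0.05 this gives d = 0.815, the printed value. All 16 entries of Table 1 come back to within 0.001 (H1.2 uses λ0 = 0.70 and y = 16.6 reports). Table 1 is therefore a unit-level calculation of reports over unit patient-days. It allows for no lost reports.

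**2. H1.1 with category A reports lost.** Assumption: a share q of the added reports on SAFE Loop units is category A, with none at baseline or in control. The model then sees d(1 − q). Power = Φ(d(1 − q)·√(9/V) − 1.960), where V is the bracketed variance at the reduced λ1.

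| q of added reports | Rise seen | λ1 | V | Rise × √(9/V) | Power |
|---|---|---|---|---|---|
| 0 | 0.815 | 3.075 | 0.761 | 2.803 | 80% |
| 10% | 0.73 | 2.99 | 0.749 | 2.543 | 72% |
| 25% | 0.61 | 2.87 | 0.730 | 2.146 | 57% |
| 50% | 0.41 | 2.67 | 0.700 | 1.461 | 31% |

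As a share of all SAFE Loop reports in the period, these rows are small: 0.815q/3.075 = 2.7%, 6.6% and 13%.

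The same formula at CV 0.01 (d = 0.794, true rate ratio 3.054/2.26 = 1.351), with the loss set as a share of all reports:

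| Control and baseline share | SAFE Loop share | Ratio seen | Power |
|---|---|---|---|
| 0 | 5% | 1.28 | 63% |
| 0 | 10% | 1.22 | 43% |
| 0 | 20% | 1.08 | 10% |
| 5% | 5% | 1.351 | 78% |

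The last row shows that the harm comes from a difference between arms, not from loss as such.

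**3. H1.2 under complete-case fitting.** Take CV 0.01 and d = 0.299, so the true SAFE Loop mean is 0.999 factors per report. Assume 20% of SAFE Loop reports are dropped and carry r times the factors of the patient-linked ones. The mean seen is 0.999/(0.8 + 0.2r), with 16.6 × 0.8 = 13.3 reports per SAFE Loop unit.

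- r = 1.5: 0.999/1.10 = 0.908. The difference shrinks to 0.208 and power is 47%.
- r = 1: the difference stays at 0.299 and power is 74%, a loss of precision only.
- r = 0.5: 0.999/0.90 = 1.110. The difference is overstated at 0.410.

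Nothing in the documents gives r, so the direction of any H1.2 bias is unknown.

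**4. Passages side by side.** The descriptive rate and Table 1 both keep a no-patient report. The H1.1 model cannot, and the H1.2 model keeps it only if the covariates are set aside. The planned analysis therefore departs from the plan's own rate definition and power basis.

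**The case against.** The case against has several sound parts.

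- **Eligibility.** Target Medication Events are errors and adverse events. Table 10, used for Aim 3, covers NCC MERP B to I and leaves out A. On that reading category A reports lie outside H1.1 by definition, and leaving them out is no bias. Table 6 is a severity scale used descriptively, not an eligibility rule. This stands as an ambiguity: section 6.1.1 teaches unsafe-condition reporting within the same Target Medication Event training, so the plan must say which applies. The H1.2 definition carries no such limit.
- **Which model is built on patients.** A reader might infer that both Aim 1 models are. The documents do not support that: only H1.1 counts per patient. H1.2 loses reports solely through its covariates, and complete-case fitting is an assumption, since section 9.4.2 is silent.
- **Differential loss.** A reader might take it as established that reports vanish mainly in the intervention arm. The training makes this plausible, but no share is given for either arm. Section 6.1.1 sends the online module to all nurses on study units, without limiting it to SAFE Loop units, and section 2.3.1 stresses near misses and no-harm events rather than hazards.
- **Volume.** Section 2.3.1 treats incident reports as carrying patient identifiers, and the synopsis states the Aim 1 size as 1,663 patients. Category A may be rare.
- **Already planned.** Section 9.4.2 tabulates NCC MERP percentages by arm for baseline and intervention periods, so the category A share will be visible.

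These points limit the size and certainty of the problem. They do not supply a rule for a report that the stated models cannot hold.

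**Conclusion.** The concern holds in limited form. As written, the H1.1 model cannot include a report without a patient, and the H1.2 model would drop one under complete-case fitting, although the descriptive rate and Table 1 would keep both.

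For H1.1 the bias is toward no effect, and only to the extent that category A reports qualify as Target Medication Events and are more frequent on SAFE Loop units. Power of 72%, 57% or 31% rests on assumed shares of 10%, 25% or 50% of the added reports, with none at baseline or in control. For H1.2 a reader might infer attenuation, on the view that hazard reports are rich in system factors. The documents do not show this, and the bias could equally inflate the effect.

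This should be fixed because it is cheap and because settling the rule after the reports have been seen could sway a primary result. It is not a must-fix: the share is unknown and the model that excludes these reports outright serves a secondary endpoint.

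A separate matter is that the covariates are "models will adjust for demographics, Elixhauser comorbidity index, and primary payer (collected under Aim 3"), where 1,520 hospitalizations are sampled from the baseline and follow-on periods. Repairing that source would not help here, because no source can supply patient values for a category A report.

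**What to change.** Amend section 9.4.2 before Aim 1 data are analysed:

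1. Reconcile the Target Medication Event definition and training text in section 6.1.1 with Tables 6 and 10 in section 8.1. State whether a category A report that addresses a Target Medication Event counts for H1.1. Do not widen H1.1 beyond Target Medication Event reports.
2. Model H1.1 as the count of eligible reports per nursing unit and period, with offset log(unit patient-days/1000), keeping arm, period, step and the nursing-unit random effect. This matches Table 1, which then needs no change on this account.
3. Fit the primary H1.2 model on all eligible medication reports with arm, period, step and a nursing-unit random effect, without patient covariates. Give the patient-adjusted model on patient-linked reports as a sensitivity analysis.
4. Use the NCC MERP percentages already planned by arm and period to show the category A share beside both results.

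No new data are needed. The cost is that the primary Aim 1 models give up patient-level adjustment, so any imbalance in patient mix between arms is handled only by the randomised, blocked design and the baseline comparison.
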